8.3 Primary Efficacy Endpoint(s) and Analyses

8.3.1 Primary Efficacy Endpoint(s)

The primary endpoint of this study is the proportion of subjects who achieve clinical remission per Adapted Mayo score (defined as stool frequency subscore ≤ 1 and not greater than baseline, rectal bleeding subscore of 0, and endoscopic subscore ≤ 1) at Week 12.

8.3.2 Handling of Missing Data for the Primary Efficacy Endpoint(s)

Subjects with missing primary endpoint data at Week 12 will be classified as "not achieved" (non-responder imputation [NRI] method) for the primary analysis.

8.3.3 Primary Efficacy Analysis

For Sub-Study 1 – Induction Period 1:

The dose-response relationships among the three risankizumab dose groups (600 mg, 1200 mg and 1800 mg) and placebo group will be characterized for the primary endpoint at Week 12 using Multiple Comparison Procedure - Modeling (MCP-Mod)^{1,2} approach based on ITT1A population. The response based on the primary analysis approach NRI will be used, and ADDPLAN DF software will be used to perform the MCP-Mod analyses.

A set of 5 pre-specified standardized candidate dose-response models (including log-linear, E_{max} , exponential, logistic and $sigE_{max}$) will be utilized to examine the dose-response relationship. A statistically significant dose response relationship will be declared if at least one model is identified by the MCP-Mod method to be statistically significant at $\alpha = 0.05$ (one-sided). The fitted dose response curves will be presented graphically for all statistically significant models along with confidence bands. The minimum effective dose (MED) will be identified for each statistically significant model based on the pre-specified clinical meaningful target. The weighted MED across all significant models will be calculated, with weight being inverse of model AIC.

The pairwise comparison between the treatment groups will also be performed using the Cochran-Mantel-Haenszel (CMH) test stratified by baseline corticosteroid use and baseline Adapted Mayo score (≤ 7 and > 7) with one-sided alpha level of 0.05. A two-sided 90% confidence interval for the difference between treatment groups and placebo will be constructed. There will be no multiplicity adjustment for the pairwise comparison. The goal of the CMH test is to provide an estimation of the effect size for each dose to inform the dose selection for Phase 3, not for statistical inference purposes.

Descriptive statistics based on ITT1B will be provided as an exploratory analysis. NRI will be used as imputation method.

8.3.4 Additional Analyses of the Primary Efficacy Endpoint(s)

The following sensitivity analyses for the primary endpoint of clinical remission will be conducted:

- The primary analysis will be repeated using a hybrid multiple imputation method. Subjects who discontinue study drug prior to Week 12 due to lack of efficacy or adverse events will be considered as "not achieved" for the clinical remission. Subjects who discontinue for other reasons will be categorized according to multiple imputations.
- An analysis of observed cases, which excludes those subjects with missing data at scheduled assessment visits.

8.4 Secondary Efficacy Analyses

Sub-Study 1 – Induction Period 1:

For Induction Period 1 in Sub-Study 1, the ranked secondary and non-ranked secondary efficacy variables listed in Section 3.2 will be analyzed by treatment group for ITT1A as the primary analysis at the nominal α level of 0.05 (one-sided).

Continuous secondary efficacy variables will be analyzed using a Mixed-Effect Model Repeated Measures (MMRM) method. It will be used for primary inference purpose. Analysis of Covariance (ANCOVA) model using LOCF imputation method will be applied as sensitivity analysis.

Categorical secondary efficacy variables will be analyzed using the CMH test controlling for stratification variables. NRI imputation will be used for primary inference purpose and observed case analyses will be used for sensitivity analysis.

Additional exploratory analysis based on ITT1B will be provided for all ranked secondary efficacy variables: continuous secondary efficacy variables will be analyzed using MMRM method and descriptive statistics will be provided for categorical secondary efficacy variables with NRI imputation method.

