8.1.6.2 Secondary Efficacy Variables

Sub-Study 1 – Induction Period 1:

For Induction Period 1 in Sub-Study 1, the secondary efficacy variables listed in Section 5.3.3.2 were analyzed by treatment group for ITT1A as the primary analysis at the nominal α level of 0.05 (one-sided).

Categorical secondary efficacy endpoints were analyzed using CMH controlling for stratification variables. NRI imputation were used for primary inference purpose except for occurrence of hospitalization and UC-related surgeries of which as observed data were used. Continuous secondary efficacy endpoints were analyzed using a Mixed-Effect Model Repeated Measures (MMRM) method as the primary analysis.

Additional analysis based on ITT1 with additional subjects enrolled into risankizumab 1800 mg IV will be conducted separately as exploratory purpose.

No multiplicity adjustment will be performed.

Sub-Study 2 – Induction Period 1:

The secondary efficacy endpoints will be compared between the subjects in risankizumab dose group and placebo group based on ITT2.

Categorical secondary efficacy endpoints will be analyzed using the same CMH test as that for primary endpoint as specified in Section 8.1.6.1.1. NRI-MI, as defined in Section 8.1.2, will be the primary approach for missing data handling in the analyses of

categorical secondary efficacy endpoints except for UC-related hospitalization, of which AO data will be used.

Continuous secondary efficacy endpoints will be analyzed using RTB-MI as defined in Section 8.1.2 with MMRM (for endpoints with more than one post-baseline visits) or with ANCOVA (for endpoints with one post-baseline visit) models.

For all endpoints specified in Section 5.3.3.2, descriptive summary will be provided for ITT1_P2 and ITT2_P2 for exploratory purposes.

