3.2 Secondary Endpoint(s)

The secondary endpoints for Sub-Study 1 are:

Ranked Secondary Endpoints:

1. The achievement of endoscopic improvement at Week 12
2. The achievement of clinical remission per Full Mayo score at Week 12 in subjects with a Full Mayo score of 6 to 12 at Baseline
3. The achievement of clinical response per Adapted Mayo score at Week 12
4. The achievement of clinical response per Partial Adapted Mayo score at Week 4
5. The achievement of endoscopic remission at Week 12
6. Occurrence of hospitalizations through Week 12
7. The achievement of mucosal healing at Week 12
8. Change from Baseline in UC-Symptom Questionnaire (UC-SQ) at Week 12
9. Change from Baseline in Inflammatory Bowel Disease Questionnaire (IBDQ) at Week 12
10. Change from Baseline in Short Form-36 at Week 12
11. Change from Baseline in Functional Assessment of Chronic Illness Therapy-Fatigue (FACIT-F) at Week 12
12. UC-related surgeries through Week 12

Non-Ranked Secondary Efficacy Endpoints:

- The achievement of SFS = 0, RBS = 0, and endoscopic subscore = 0 at Week 12
- The achievement of SFS \leq 1 over time
- The achievement of RBS = 0 over time
- Change from Baseline in Partial Adapted Mayo score over time
- Change from Baseline in Full Mayo score at Week 12
- Change from Baseline in SFS over time
- Change from Baseline in RBS over time
- Change from Baseline in hs-CRP over time

- Change from Baseline in FCP over time
- Change from Baseline in Ulcerative Colitis Endoscopic Index of Severity (UCEIS) at Week 12
- The achievement of histologic remission at Week 12
- Change from Baseline in European Quality of Life 5 Dimensions (EQ-5D-5L) over time
- Change in Work Productivity and Impairment Questionnaire – UC (WPAI-UC) over time
- Time to clinical response per partial adapted Mayo score
- Change from baseline in Patient Global Impression of Severity (PGIS) over time
- Patient Global Impression of Change (PGIC) over time
- The achievement of clinical remission per Adapted Mayo over time
- The achievement of endoscopic improvement over time
- The achievement of endoscopic remission over time
- The achievement of no bowel urgency at Week 12
- The achievement of no abdominal pain at Week 12
- Achieving response in IBDQ bowel symptom domain (increase of IBDQ bowel symptom domain score ≥ 6 from baseline) at Week 12
- Change from Baseline in subject-reported stool frequency (absolute values)

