8.2 Handling of Missing Data

UC-related corticosteroids Censoring

For both Periods 1 and 2, the following subjects will be censored for efficacy assessments from that point through the end of the study.

- subjects not on UC-related corticosteroids (systemic or locally acting corticosteroids for UC) at Baseline who then initiated during the study or
- subjects on UC-related corticosteroids who have dosages increased to greater than the dose taken at Baseline.

I.e., these subjects will be considered as 'Not Achieved' for binary endpoints (Y/N) and any non-missing continuous assessments after censoring will not be used in the analysis

For composite endpoint, censoring will be applied on each component before calculating the composite endpoint. If any component is censored, the composite endpoint will be considered as censored. These subjects will continue to be evaluated in the safety population. In addition, hospitalizations and UC-related surgeries will not be censored.

Handling of Missing Data

Missing data will be imputed using the following methods for the efficacy analyses.

- Observed Cases (OC): The OC analysis will not impute values for missing evaluations, and thus a subject who does not have an evaluation on a scheduled visit will be excluded from the OC analysis for that visit. All the other imputations will be performed after OC.
- Non-Responder Imputation (NRI): The NRI approach is used for binary efficacy variables. These variables can take values of 'Achieved' or 'Not Achieved' or may be. According to the NRI approach, all missing values will be considered as 'Not Achieved.'
- Last Observation Carried Forward (LOCF): The LOCF analyses will use the completed evaluation from the previous visit for efficacy measures assessed to impute missing data at later visits. Baseline and Pre-Baseline value will not be used for the imputation. If there are no non-missing values after the Baseline, then the LOCF value also will be missing.

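### The Sub-Study 1 SAP makes non-responder imputation primary for hospitalizations and UC-related surgeries too, where the protocol uses as-observed data

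*SAP*

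**What the plan says.** The Sub-Study 1 SAP (Version 6.0) lists "Occurrence of hospitalizations through Week 12" as ranked secondary endpoint 6 and "UC-related surgeries through Week 12" as ranked secondary endpoint 12 (Section 3.2). Both are categorical, and in both the event is unfavourable.

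Section 8.4 sets one missing-data rule for categorical secondary variables in ITT1A: "Categorical secondary efficacy variables will be analyzed using the CMH test controlling for stratification variables. NRI imputation will be used for primary inference purpose", with observed cases as the sensitivity analysis. The ITT1B paragraph of the same section also applies non-responder imputation (NRI) to the ranked categorical endpoints. Neither paragraph names an exception.

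Section 8.2 gives the scope of NRI, "The NRI approach is used for binary efficacy variables", and its effect: "According to the NRI approach, all missing values will be considered as 'Not Achieved". The same section says of the two endpoints: "In addition, hospitalizations and UC-related surgeries will not be censored". That sentence belongs to the paragraph on corticosteroid censoring.

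Protocol Section 8.1.6.2, on Sub-Study 1, reads: "NRI imputation were used for primary inference purpose except for occurrence of hospitalization and UC-related surgeries of which as observed data were used". The protocol synopsis makes the same exception.

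**The concern.** NRI is a cautious choice when achieving the endpoint is good, because a subject with no data is denied the benefit. When the endpoint is a harm, not achieved is the favourable outcome, and the same rule credits a subject with no data as free of the event. The event rate in each arm then falls as missingness rises. If missingness differs between arms, the comparison shifts for a reason unrelated to hospitalization or surgery.

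The SAP also departs from the protocol on these two endpoints without saying so. A reader of the SAP would expect NRI as the primary analysis and observed cases as sensitivity; a reader of the protocol would expect as-observed data as primary.

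**Working it through.** **1. Is there an exception elsewhere in the Sub-Study 1 SAP?**

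- The sentence in Section 8.2 that protects the two endpoints concerns steroid censoring. It keeps events that occur after a steroid change and says nothing about missing data.
- Section 1.0 says that changes from the analyses in protocol Amendment 2 are outlined in Section 13.0. That version history lists no change to missing-data handling for these endpoints, so no deliberate departure is recorded.
- The separate Sub-Study 2 SAP, Section 9.2.1, does carve out hospitalization and UC-related surgeries and analyses them as observed.

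The exception is therefore absent where it is needed and present in the sister document.

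**2. What does the rule do to a rate?**

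The documents state no event rate, missing fraction or power for either endpoint, so there is no figure to reproduce. All rates and counts below are assumed; only the 60 subjects per arm come from the documents (SAP Section 2.3).

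Let p be the event rate among observed subjects and d the missing fraction.

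- As observed: rate = events / observed = p
- NRI, with not achieved read as no event: rate = events / all subjects = p × (1 − d)

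With p = 8%:

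- d = 10%: 8% × 0.90 = 7.2%, which is 0.8 points below as-observed
- d = 15%: 8% × 0.85 = 6.8%, which is 1.2 points below as-observed

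In a 60-subject arm these gaps amount to 0.008 × 60 = 0.5 and 0.012 × 60 = 0.7 of a subject.

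**3. What does it do to a comparison?**

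- *No true difference, equal missingness.* The spurious difference is 0.
- *No true difference, p = 10% in both arms, 20% missing on placebo and 5% on active.* Placebo is 10% × 0.80 = 8.0% and active is 10% × 0.95 = 9.5%, a spurious 1.5 points against active. With the missing fractions exchanged, the same 1.5 points favour active.
- *Observed rates of 15% on placebo and 5% on active, same missingness (20% and 5%).* The as-observed difference is −10.0 points. Under NRI it is 5% × 0.95 − 15% × 0.80 = 4.75% − 12.0% = −7.25 points.

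**4. How much depends on the reading of not achieved?**

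Assume 60 per arm, with 6 events in 48 observed on placebo (12 missing) and 2 events in 57 observed on active (3 missing).

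| Rule | Placebo | Active | Difference |
|---|---|---|---|
| As observed (protocol) | 6/48 = 12.5% | 2/57 = 3.5% | −9.0 points |
| Missing = no event | 6/60 = 10.0% | 2/60 = 3.3% | −6.7 points |
| Missing = event | 18/60 = 30.0% | 5/60 = 8.3% | −21.7 points |

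Neither imputed version matches the protocol, and the two lie far apart.

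**The case against.** **The direction is not certain.** Section 8.2 describes variables that are achieved or not achieved, and these two endpoints are not worded as achievements. Protocol Section 8.1.2 calls missing subjects non-responders, which for a harm could mean that they had the event. This stands: event-free is the most literal reading, not a stated rule. It does not remove the conflict, because either reading imputes where the protocol does not.

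**The loss may be small.** Hospitalization is a criterion for a serious adverse event, and adverse events are collected until 140 days after the last dose. A subject who stops treatment early is therefore not automatically missing for events through Week 12. This also stands, and real missingness may be well below the assumed fractions.

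**A reader might infer a much larger understatement.** If those missing carried an assumed risk of 20–30%, the true rate in the examples would be 6.8% + 0.15 × 20% = 9.8%, or 7.2% + 0.10 × 30% = 10.2%. NRI would then sit 3 points too low. The documents do not support charging that gap to the SAP. The risks are assumed, and the as-observed rule that the protocol prescribes would still give 8.0%, which is 1.8–2.2 points short. Only 0.8–1.2 points separate the two rules.

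**A reader might also infer that the reported results are wrong.** The protocol says in the past tense that as-observed data were used, so the tables may already be right and the SAP text alone at fault. Section 8.4 also plans an observed-case analysis as sensitivity. Because the two endpoints escape steroid censoring, that is in substance the protocol's primary analysis with the labels exchanged.

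**Conclusion.** The inconsistency is real and is not resolved anywhere in the Sub-Study 1 SAP. As written, Section 8.4 applies NRI as the primary method to two harm endpoints that the protocol exempts. On the most literal reading, missing subjects count as event-free.

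The size cannot be determined from the documents. Under the stated assumptions the shift within an arm is about one point, less than one subject in 60. The effect on a comparison depends on how unequal the missingness is and can go either way.

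The consequences are contained. Sub-Study 1 is the Phase 2b part, its secondary tests are nominal with no multiplicity adjustment (SAP Section 12.0), and its efficacy data are not combined with Phase 3 for inference (protocol Section 5.6.1). The point should be corrected because the primary rule for two ranked endpoints is contradictory and ambiguous; it does not threaten a main conclusion.

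**What to change.** In Section 8.4 of the Sub-Study 1 SAP, in both the ITT1A and the ITT1B paragraphs, add wording to this effect: *NRI, except for hospitalizations and UC-related surgeries. These are analysed as observed: every event recorded through Week 12 counts whether or not steroids were changed, and a subject without an evaluation is left out of the denominator and not imputed.* This agrees with protocol Sections 8.1.2 and 8.1.6.2 and with Section 9.2.1 of the Sub-Study 2 SAP.

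The denominator must be stated. Saying only that recorded events are counted and nothing is imputed, while dividing by all ITT1A subjects, gives the same number as missing = no event. Protocol Appendix C schedules no separate hospitalization assessment, so the text should also say when a subject counts as having no evaluation.

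The cost is one sentence in two paragraphs, an entry in the version history, and a check of which rule produced the two reported tables. Rerun them only if NRI was used.

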8.5 Additional Efficacy Analyses

The efficacy analysis for subjects who were randomized and received at least one dose of risankizumab during the Induction Period 1 in Sub-study 1 (both ITT1A and ITT1B populations) and the Induction Period 2 in Sub-Study 1 (ITT1_P2 population) will be performed for exploratory purpose at the nominal α level of 0.05 (two-sided).

Definition of Time to Event (Clinical Response Per Partial Adapted Mayo Score)

Time to event is defined as number of days from the date of the first dosing to the date of the first occurrence of an event. It is calculated as (date of first occurrence of Event – date of the first dosing + 1). Subjects who discontinue from study prior to experiencing the

event are censored at the time of discontinuation. Subjects who are not experiencing the event are censored at the date of last non-missing measurement of partial adapted Mayo score. Pairwise comparison between each treatment group and placebo will be performed by log-rank test and Cox proportional hazards regression analysis including treatment and baseline stratification factors as covariates.

Time to event analysis will be based on OC data.

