9.5 Additional Efficacy Endpoints and Analyses

9.5.1 Additional Analyses

All additional binary efficacy endpoints specified in Section 3.3 will be analyzed based on ITT2 using the same approach as the primary approach for primary endpoint as specified in Section 9.3.2. Specifically, CMH adjusting for stratification factors will be used to construct the treatment difference, the associated 95% CI and p-value between risankizumab 1200 mg IV group and placebo group. The NRI-MI will be the primary approach for missing data handling in the analyses of binary secondary efficacy endpoints except for the occurrence of UC-related hospitalization.

All additional continuous endpoints will be analyzed based on ITT2 by RTB-MI and the corresponding analyses are specified in Section 9.2.2. The least square (LS) mean and 95% CI for each randomized treatment group and the LS mean treatment difference, the associated 95% CI and the p-value between risankizumab 1200 mg IV group and the placebo group will be provided. For time to clinical response per Partial Adapted Mayo score in Period 1, the distribution of time to clinical response including median will be estimated for each treatment group using Kaplan-Meier method and compared between the two treatment groups using stratified Log-rank test. The hazard ratio and corresponding 95% CI between the two treatment groups will also be obtained using the Cox Proportional Hazard Model. Subjects who have experienced IE2 or IE3 prior to experiencing the event (clinical response per Partial Adapted Mayo) are censored at the time of the earliest intercurrent event of IE2 or IE3. Subjects who are not experiencing the event (clinical response per Partial Adapted Mayo) are censored at the date of study discontinuation (if discontinued in Period 1) or last non-missing measurement of partial adapted Mayo score in Period 1 (if not discontinued in Period 1).

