2.3 Treatment Assignment and Blinding

Sub-Study 1 (Phase 2b Induction):

Induction Period 1:

Subjects (n = 240) who meet all of the inclusion criteria and none of the exclusion criteria will be randomized into the study in a 1:1:1:1 ratio to one of the following treatment groups:

- Group 1: Risankizumab 1800 mg IV Weeks 0, 4, 8 (n = 60)
- Group 2: Risankizumab 1200 mg IV Weeks 0, 4, 8 (n = 60)
- Group 3: Risankizumab 600 mg IV Weeks 0, 4, 8 (n = 60)

- Group 4: Placebo IV Weeks 0, 4, 8 (n = 60)

The randomization at baseline will be stratified by baseline steroid use (yes vs no) and baseline Adapted Mayo score (≤ 7 vs > 7). Endoscopy and evaluation of clinical response and remission will occur at Week 12.

Induction Period 2:

At Week 12, subjects who do not achieve clinical response will be randomized by Interactive Response Technologies (IRT) to Induction Period 2, a double-blind, double-dummy 12-week treatment period to evaluate reinduction with risankizumab versus starting maintenance dosing on clinical response status.

Subjects who received IV risankizumab induction will be randomized 1:1:1 to:

- Group 1: 1800 mg IV risankizumab Weeks 12, 16, 20
- Group 2: 360 mg SC risankizumab Weeks 12, 20
- Group 3: 180 mg SC risankizumab Weeks 12, 20

Subjects who received IV placebo induction treatment will receive:

- Group 4: 1800 mg IV risankizumab Weeks 12, 16, 20

Subjects randomized in Groups 1 and 4 will receive placebo SC and subjects randomized in Groups 2 and 3 will receive placebo IV, in order to keep the blind. The IV risankizumab dose or matching IV placebo will be given at Weeks 12, 16, and 20. The SC risankizumab dose or matching SC placebo will be given at Weeks 12, and 20.

Dose Selection Analysis:

During this analysis, Sub-Study 1 will continue to enroll additional subjects in the 1800 mg dosing group, on an open-label basis, to avoid interrupting the study activities

during the analysis period and to generate a sufficient number of subjects with clinical response to be enrolled into the maintenance Study M16-066.

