2.4 Sample Size Determination

Sub-Study 1 (Phase 2b):

For Sub-Study 1 (Phase 2b portion of the study), approximately 240 subjects in the Bio-IR population will be equally randomized using a 1:1:1:1 ratio to three risankizumab treatment groups (600 mg, 1200 mg and 1800 mg IV Q4W) and the placebo group. The sample size for this study is based on the expected proportion of subjects who achieve clinical remission per Adapted Mayo Score at Week 12. Assuming clinical remission rate of 7% in the placebo arm and maximum of 25% in at least one of the risankizumab treatment groups at Week 12, a sample size of 60 subjects per treatment group is sufficient to test for the presence of a dose response signal, to select the best dose response model for the observed data out of a pre-specified set of candidate models, and to estimate target doses of interest (e.g., MED) via modeling using MCP-Mod (Multiple comparison procedure and modeling) approach.^{1,2} The assumptions for the rates of clinical remission were estimated based on the meta-analysis of Phase 3 induction studies of the marketed drugs for patient population who have had intolerance or inadequate response to prior biologic therapy. This approach provides an average power of approximately 87% to detect a dose effect at 5% level of significance (one-sided) with the linear, E_{max} ($ED_{50} = 600$ per dosing visit), exponential ($\delta = 600$ per dosing visit), logistic ($ED_{50} = 600$ per dosing visit and $\delta = 160$) and $sigE_{max}$ ($ED_{50} = 600$ per dosing visit and $h = 3$) models pre-specified as likely candidates to characterize the dose response for risankizumab for the primary endpoint of clinical remission at Week 12 per Adapted Mayo Score.

A minimum of 240 subjects will be enrolled into Study M16-067 Sub-Study 1 for dose selection analysis. The additional subjects enrolled during the dose selection analysis period will not be part of the dose selection analysis, but will be evaluated separately as exploratory in the final CSR.

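### The Sub-Study 1 log-rank test for time to clinical response leaves out the randomisation strata that the CMH, MMRM and Cox analyses use

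*SAP*

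**What the plan says.** Section 2.3 of the Sub-Study 1 SAP sets the design: "The randomization at baseline will be stratified by baseline steroid use (yes vs no) and baseline Adapted Mayo score", the score being split at 7. That gives 2 × 2 = 4 strata.

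The same SAP then uses these factors in most of its comparative analyses:

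- the pairwise CMH test of the primary endpoint (Section 8.3.3) and the CMH tests of the categorical secondary endpoints (Section 8.4);
- the MMRM for continuous endpoints (Section 8.2);
- the Cox model for time to clinical response per Partial Adapted Mayo score (Section 8.5), with the stratification factors as covariates.

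The log-rank test stands in the same sentence as the Cox model: "Pairwise comparison between each treatment group and placebo will be performed by log-rank test". The mention of stratification factors as covariates belongs to the Cox regression, since a log-rank test has no covariates. Nothing in the section calls the log-rank test stratified.

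For the same endpoint, Section 9.5.1 of the Sub-Study 2 SAP has the arms "compared between the two treatment groups using stratified Log-rank test". Neither SAP gives a reason for the difference.

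**The concern.** When randomisation is stratified, each arm has nearly the same mix of strata by design, so differences between strata add almost nothing to the true sampling variation of the treatment contrast. An unstratified log-rank test pools all subjects into one risk set at each visit, and its variance formula still counts those differences. If the factors are prognostic, the standard error is too large: the test rejects too rarely under the null and has less power under the alternative.

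Two things are at stake. One is sensitivity to a difference in time to response at each dose. The other is coherence: each dose would carry a log-rank p-value without the strata and a Cox result with them. The two can disagree, and the plan does not say which one to read.

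**Working it through.** **Inputs from the documents.** Allocation is "equally randomized using a 1:1:1:1 ratio" with "a sample size of 60 subjects per treatment group" (Sub-Study 1 SAP, Section 2.4), so each pairwise comparison is 60 v 60. There are four strata (Section 2.3). The level is two-sided 5%, as Section 8.5 states. Partial Adapted Mayo is scored at Weeks 4 and 8, and its components are also available at Week 12 (Protocol, Appendix C).

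**Assumptions, not in the documents.** Equal strata, 15 per arm per stratum. Treatment hazard ratio for response 1.8. Placebo cumulative hazard 0.20 per 4 weeks, which with no stratum effect gives 1 − exp(−0.60) = 45% responding by Week 12. Each factor multiplies the hazard by 1, 1.5, 2 or 3.

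**Step 1: the plan's own power figure.** The plan gives no power for the log-rank test. It does give one for MCP-Mod: "average power of approximately 87% to detect a dose effect at 5% level of significance (one-sided"), for a "clinical remission rate of 7% in the placebo arm and maximum of 25% in at least one" of the dose groups. A multiple-contrast calculation with no strata (risk scale, pooled variance, the Section 2.4 shape parameters) gives 87.7% with a linear candidate shape, 87.1% with log(d+1) and 87.3% with log(d+600). Both linear and log forms were tried because Section 2.4 lists linear and Section 8.3.3 lists log-linear. The stated 87% is therefore the power of an unadjusted test.

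**Step 2: the log-rank statistic.** At visit t let d be the number of responders, n the number at risk, and n1 and n0 the numbers at risk by arm. Then

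E_t = d·n1/n, V_t = d·(n1/n)·(n0/n)·(n − d)/(n − 1), Z = Σ(d1 − E_t)/√ΣV_t.

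The unstratified test forms these terms once per visit over all 120 subjects. The stratified test forms them within each stratum and sums over strata and visits.

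**Step 3: simulation, unstratified against stratified.**

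| Assumed HR per factor | Type I error, unstratified | Type I error, stratified | Power, unstratified | Power, stratified | Power lost |
|---|---|---|---|---|---|
| 1 | 5.2% | 5.3% | 65.8% | 65.5% | −0.3 |
| 1.5 | 4.6% | 5.1% | 64.2% | 65.9% | 1.7 |
| 2 | 4.1% | 5.2% | 59.6% | 65.8% | 6.2 |
| 3 | 2.7% | 5.1% | 48.5% | 64.4% | 15.9 |

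The stratified test holds its level throughout. With no stratum effect it costs about 0.3 points.

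**Step 4: does the same argument reach MCP-Mod?** Average power, unadjusted then stratified, by assumed odds ratio per factor:

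| OR per factor | Unadjusted | Stratified | Gain |
|---|---|---|---|
| 1 | 90.3% | 90.5% | 0.2 |
| 1.5 | 90.3% | 90.7% | 0.4 |
| 2 | 90.5% | 91.2% | 0.7 |
| 3 | 90.9% | 92.3% | 1.4 |
| 4 | 91.2% | 93.2% | 2.0 |

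These runs use binomial data with an estimated pooled variance and so sit above 87%. Only the differences should be read, and they are small.

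**The case against.** **Little may turn on the log-rank test.** A stratum-adjusted Cox comparison at each dose is already planned in the same sentence. Section 3.2 lists time to response as a non-ranked secondary endpoint, Section 8.5 describes its analyses as exploratory at a nominal level, and Section 12.0 applies no multiplicity adjustment. No decision is tied to this p-value. All of that stands, and it limits the weight of the point. It does not explain why the log-rank test departs from its neighbours and from the Sub-Study 2 plan.

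**The loss is conditional.** No document says how prognostic the two factors are, and at a hazard ratio of 1.5 per factor the loss is under 2 points. That also stands, which is why a range is given.

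**A reader might infer that the primary MCP-Mod test is underpowered for the same reason, or that dose selection suffered.** The documents do not support either reading.

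- On MCP-Mod, Section 8.3.3 says "The response based on the primary analysis approach NRI will be used, and ADDPLAN DF software will be used" for the analysis. It is silent on covariates and does not exclude them.
- The stated 87% already belongs to an unadjusted test, so no planned power is lost. The gain from adjustment is about 0.2 to 2 points.
- The SAP version history records that the MCP-Mod section was revised after regulatory feedback, so changing its model and software would be a trade-off.
- The dose choice in Protocol Section 5.6.4 rests on efficacy, exposure-response and safety, and cites pairwise nominal p-values for remission. The planned pairwise test of remission is the stratified CMH test. Time to response is not mentioned there.

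**A reader might also fear false positives.** The direction is the opposite: the unstratified test is conservative.

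**Conclusion.** The point holds for the log-rank test in Section 8.5 of the Sub-Study 1 SAP and goes no further. The test omits strata that the design and the neighbouring analyses use. The cost runs from nothing, if the strata are not prognostic, to about 16 points of power at a hazard ratio of 3 per factor, with the type I error as low as 2.7%. These sizes rest on the assumed stratum effects, treatment hazard ratio, placebo response rate, equal strata and exact balance. The direction does not depend on the particular values, provided the strata are prognostic.

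The validity of Sub-Study 1 is not in question, and neither is the dose taken into Sub-Study 2. The practical effect is on how the time-to-response p-values are reported and read.

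**What to change.** In Section 8.5 of the Sub-Study 1 SAP, specify a log-rank test stratified by baseline corticosteroid use (yes vs no) and baseline Adapted Mayo score (≤ 7 vs > 7). This matches the adjusted Cox model beside it and the Sub-Study 2 plan. Keep the unstratified test as a sensitivity analysis.

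The cost is one change of wording and routine programming, with no new data. If the strata turn out not to be prognostic, the loss of power is negligible. The Protocol (Section 5.1) reports that the 240 randomised subjects completed Week 12 and that the dose-selection analysis was done. Any stratified result added now should therefore be labelled post hoc and shown beside the planned one.

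Leave the primary MCP-Mod analysis as planned. A covariate-adjusted version is at most an optional supplementary analysis.
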